#### **6.1.1.7 Pregnancy Tests**

A serum pregnancy test may be performed by the site personnel for all females of childbearing potential (subjects  $\geq 10$  years of age) Study/Day 180 and at unscheduled visits and at the Investigator's discretion, as needed. Details on pregnancy testing requirements are located in [Appendix 7](#).

#### **6.1.1.8 Laboratory Evaluations**

A designated laboratory (or laboratories) will perform the analyses of all specimens collected. Collection, shipment of samples, and reporting of results by the central or local (if needed) laboratory (or laboratories) will be detailed in the laboratory manual provided to the Investigators. If age/weight of the patient does not allow for this additional blood volume, then values from local labs will serve as the Day 160 values used for the present study. The laboratory tests to be performed for subjects in this study are listed in [Table 7](#).

If necessary, laboratory assessments may be performed by a laboratory other than the designated central laboratory. In this case, normal ranges of test values for this laboratory should be provided to the sponsor.

The Investigator at each site is required to review all clinically relevant laboratory results requested in the protocol and to record those results in the CRF. The diagnosis associated with any clinically significant laboratory abnormalities should be recorded as an (S)AE on the CRF.

### 6.1.1.9 Assessment of Ectopic Tissue Formation

To detect any ectopic tissue formation, a radiologist and an Investigator at each study site may compare the optional CT scan or MRI performed during screening for MSB-GVHD001 with the optional CT scan or MRI performed at end of study/Day 180 or at an unscheduled visit to determine if there is ectopic tissue formation. If applicable, the same method of radiologic scan should be used for both evaluations. If the formation of ectopic tissue is suspected, further evaluation may include MRI or positron-emission tomography (PET) scanning, and possibly biopsy.

[REDACTED]

[REDACTED]

[REDACTED]

[REDACTED]

[REDACTED]

## 6.2 Evaluation Period

Subjects will be evaluated through Day 180 from the date of initial remestemcel-L infusion in MSB-GVHD001.

## 6.3 Missing or Delayed Study Visits

Every effort should be made to ensure compliance with prescribed study visits. Missing of study visits is generally not permitted. However, in exceptional situations and with the sponsor's approval, visits may be postponed.

Subjects may be consented on MSB-GVHD002 simultaneously when being provided with the MSB-GVHD001 consent, or at any visit up through Day 180 ( $\pm 7$  days). Due to IRB/EC review times, there may be situations in which there is a delay in the IRB/EC approval for MSB-GVHD002 and the associated informed consent forms. If the IRB/EC approval for MSB-GVHD002 consent form is not available at Day 100, Day 120, Day 140, and/or Day 160, these visits will be marked as missed visits in EDC. Data collection for MSB-GVHD002 will begin once the subject has signed consent for MSB-GVHD002. The Investigator should make every effort to present the IRB/EC approved consent for MSB-GVHD002 to the subject no later than Day 180 ( $\pm 7$  days).

To ensure timely attendance at the required clinic visits, the visit schedule for the entire study period should be arranged and agreed upon with the subject at the baseline visit. The study site should document and notify the sponsor of any visits not completed within the specified time frame or within the allowable window period.

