**Table 6: Schedule of Assessments and Procedures**

	Baseline/ Visit 1	Visit 2	Visit	Visit 4	Visit 5	
Study Days	Day 100 (same as Day 100 in MSB-GVHD001)	Day 120	Day 140	Day 160	End of Study/ Day 180	
Visit window	±7 days	±5 days	±5 days	±5 days	±7 days	Unscheduled
Inclusion/exclusion criteria/informed consent a	X					
Vital signs (HR, BP, Temp, RR, oxygen saturation) b		X	X	X	X	X
Height and weight					X	X
Physical examination		X	X	X	X	X
CMV c		X	X	X	X	X
Hematology laboratory tests				X	X	X
Chemistry laboratory tests				X	X	X
Urinalysis				X	X	X
Hospitalization d						X
Acute GVHD assessment (Skin, Lower GI, Upper GI, Liver)						
Acute GVHD assessment (Skin, Lower GI, Upper GI, Liver)		X	X	X	X	X
Chronic GVHD assessment						
Chronic GVHD assessment		X	X	X	X	X
Concomitant medicationf						
Concomitant medication f		X	X	X	X	X
Transfusiong						
Transfusion g						X
Optional CT scan or MRI (Chest, Abdomen and Pelvis)l						
Optional CT scan or MRI (Chest, Abdomen and Pelvis) l					X	X
12-Lead ECG						
12-Lead ECG					X	X
Termination/end of study						
Termination/end of study					X	X
Pregnancy testl						
Pregnancy test l					X	X
Adverse event evaluationk						
Adverse event evaluation k		X	X	X	X	X

a Informed consent for MSB-GVHD002 may be provided to the subject simultaneously with the informed consent for MSB-GVHD001, or at any visit prior to Day 180 (± 7 days) .

b Vital signs include measurements of heart rate (HR), blood pressure (BP), respiratory rate (RR), and temperature (temp).

c Investigators should provide standard of care treatment for viral infections as appropriate, including prophylaxis and treatment if there is evidence of viral reactivation and/or infection

d Hospitalization with a start date after the visit window of Day 100 (Day 107) will be collected in MSB-GVDH002.

Hospitalization with a start date before the visit window of Day 100 (Day 106) will be collected in MSB-GVDH001.

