**[REDACTED]**

f Concomitant medication with a start date after the visit window of Day 100 (Day 107) will be collected in MSB-GVDH002.

Concomitant medication with a start date before the visit window of Day 100 (Day 106) will be collected in MSB-GVDH001.

g Total number of units transfused of blood product will be recorded in the eCRF during study. Transfusion with a start date after the visit window of Day 100 (Day 107) will be collected in MSB-GVDH002. Transfusion with a start date before the visit window of Day 100 (Day 106) will be collected in MSB-GVDH001

■ [REDACTED]  
■ [REDACTED]  
■ [REDACTED]  
■ [REDACTED]

j Pregnancy test will be performed on all females of childbearing potential (subjects  $\geq 10$  years of age). Guidance on childbearing potential and pregnancy testing is located in [Appendix 7](#).

k All AEs will be collected in this study. Adverse events with an onset date after the visit window of Day 100 (Day 107 – as allowed in protocol MSB-GVHD001) will be collected in MSB-GVHD002.

Adverse events with an onset date before the visit window of Day 100 (Day 106 – as allowed in protocol MSB-GVHD001) will be collected in MSB-GVHD001

l CT scans and MRI are optional and may be omitted at the discretion of the Investigator.

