## 6. STUDY PROCEDURE

### 6.1 Visit Schedule and Assessments

Table 6 lists all planned assessments, which are marked with an “X” when the visits are performed. Subjects should be seen for all visits on the designated day or at a time that is as close as possible to the designated day. The study assessment schedule in Table 6 outlines all procedures to be performed on subjects at the scheduled visits.

In order to minimize variability in evaluations, ideally, the same individuals should perform the same tests on all the subjects at a given trial site.

The following assessments and procedures will be performed at study visits:

- Informed consent. Subject may be consented on MSB-GVHD002 simultaneously when being provided with the MSB-GVHD001 consent, or at any visit up through Day 180 ( $\pm$  7 days). If the IRB/EC has not yet approved the consent for MSB-GVHD002 at Day 100 (MSB-GVHD001), the Investigator should make all efforts to have the IRB/EC approved consent for MSB-GVHD002 presented to the subject no later than Day 180 ( $\pm$  7 days). See Section 6.3 for additional information about handling of visits from Day 100 through Day 160 when an IRB/EC approved consent is not available.
- Review of inclusion / exclusion criteria
- Physical examination
- Height and weight
- Vital signs (heart rate [HR], blood pressure [BP], temperature, and respiratory rate [RR])
- GVHD assessment (skin, lower GI, upper GI, liver) using the same method as that of MSB-GVHD001
- O2 saturation by pulse oximetry (SaO2/SAT)
- Adverse event (AE) assessment
- Incidence of chronic GVHD (cGVHD) (Appendix 8)
- Survival status
- Information on hospitalization status (namely the date of hospitalization)
- Steroid dose(s)
- Prior and concomitant medications

- Laboratory assessments
  - Hematology (including CMV, please see [Table 6](#) for details)
  - Serum chemistry
  - Urinalysis
- [REDACTED]
- Optional CT scan or MRI of the chest, abdomen, and pelvis at the discretion of the investigator. Scans may contribute information with regard to baseline disease burden and may also provide baseline for evaluation of future possible ectopic tissue formation. For CT, use intravenous (IV) contrast; if IV is contraindicated for any reason, oral is acceptable even in the presence of GI GVHD.
- 12-Lead ECG
- [REDACTED]
- [REDACTED]
- [REDACTED]

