#### 6.1.1.1 Physical Examination

A physical examination, including but not limited to, examination for evidence of adverse events, will be performed at Day 120, Day 140, Day 160, the end of study/Day 180, and at unscheduled visits as needed.

Information about physical examinations must be available in the source documentation at the study site. Significant new findings made after the Day 100 visit that meet the definition of an AE or SAE must be recorded on the Adverse Event CRF.

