#### **6.1.1.6 (Serious) Adverse Events**

All (S)AEs, including those considered to have a causal relationship to the IMP, will be collected at each assessment time point. (S)AEs collected will consist of both solicited and events voluntarily reported by the subjects.

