## 7. SAFETY GUIDANCE

### 7.1 Definitions

#### 7.1.1 Adverse Event

An AE is defined by the International Conference of Harmonization (ICH) guideline for Good Clinical Practice as any untoward medical occurrence in a subject administered a pharmaceutical product and which does not necessarily have a causal relationship with the treatment.

An AE can therefore be any of the following:

- Any unfavorable and unintended sign (including an abnormal laboratory finding), symptom, or disease temporally associated with the use of a medicinal product, whether or not considered related to the medicinal product
- Any new disease or exacerbation of an existing disease (a worsening in the character, frequency, or severity of a known condition)
- Recurrence of an intermittent medical condition (e.g., headache) not present at baseline
- Any deterioration in a laboratory value or other clinical test (e.g., ECG, X-ray) that is associated with symptoms or leads to a change in study treatment or concomitant treatment or discontinuation from study drug.

Adverse events that are related to a protocol-mandated intervention, including those that occur prior to assignment of study treatment (e.g., screening procedures such as biopsies etc.) are to be reported.

Collection of all AEs will begin upon signing of the informed consent form (ICF). Pre-existing conditions that **worsen** during a study are to be reported as AEs.

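### AEs and SAEs with onset between about Day 107 and a late MSB-GVHD002 consent have no clear home in the visible text, and no look-back is set up

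*Combined protocol and SAP*

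**What the plan says.** **When consent may be given.** Section 6.1 allows MSB-GVHD002 consent together with the MSB-GVHD001 consent "or at any visit up through Day 180" (±7 days), and Section 6.3 repeats this. Table 6 footnote a instead says "or at any visit prior to Day 180" (±7 days). Section 6.3 foresees slow ethics approval and has the Day 100 to Day 160 visits entered as missed where no approved form exists.

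**When collection starts.** Section 6.3: "Data collection for MSB-GVHD002 will begin once the subject has signed consent for MSB-GVHD002". Section 7.1.1: "Collection of all AEs will begin upon signing of the informed consent form (ICF"). Section 9.4.1 says the same for AEs and SAEs. Section 8 goes further: it ties AE recording and 24-hour SAE reporting to events that occur after consent.

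**Which study an event belongs to.** Table 6 footnote k states "All AEs will be collected in this study". It assigns to MSB-GVHD002 "Adverse events with an onset date after the visit window of Day 100" (Day 107) and leaves earlier onsets (Day 106) with MSB-GVHD001. It does not mention the consent date. Footnotes d, f and g split hospitalisations, concomitant medications and transfusions in the same way.

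**Who is analysed.** The Safety Population in Section 9.2 is every treated subject who entered MSB-GVHD002, so it includes late consenters. Section 9.1 plans one presentation for the extension period alone and one for both studies together.

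**The concern.** Take a child with an SAE on Day 130 who consents on Day 160. By footnote k the event is too late for MSB-GVHD001 and belongs to MSB-GVHD002. By Section 8 it falls outside MSB-GVHD002 reporting, because it occurred before consent. No visible section says which instruction prevails or tells the site to abstract the event from the chart. Sites could therefore treat identical cases differently, or record none of them.

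Safety through Day 180 is the primary objective, and Section 2.2 itself describes the period after acute treatment as one with more opportunistic infections and other AEs. If the pre-consent days go unrecorded and the child still counts in the denominator, those days look event-free in a crude extension-period percentage. A later SAP can adjust denominators or exposure time, but it cannot recover events that were never entered.

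**Working it through.** **Plan's own figure.** Section 4.2 places the last 80 of the 180 days under MSB-GVHD002: 180 − 100 = 80, reproduced. For AEs, footnote k moves the start to about Day 107, so the extension window is 180 − 107 = 73 days.

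**Two readings of footnote k for an onset between Day 107 and consent.**

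- *It requires the event.* MSB-GVHD002 must record it, but Section 8 limits recording and reporting to events after consent. The passages conflict.
- *It only divides events between databases.* Consent is then a silent precondition. MSB-GVHD001 stops at about Day 106, MSB-GVHD002 starts at consent, and neither covers the interval.

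Both readings need a clarifying sentence.

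**Uncovered time.** Gap = consent day − 107. Ranges use the Table 6 window of ±5 days.

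| Consent at | Gap in days (range) | Share of 73 days | Share of 180 days |
|---|---|---|---|
| Day 120 | 13 (8–18) | 13/73 = 18% | 13/180 = 7% |
| Day 140 | 33 (28–38) | 33/73 = 45% | 33/180 = 18% |
| Day 160 | 53 (48–58) | 53/73 = 73% | 53/180 = 29% |

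Later consent is possible. Footnote a allows any visit before Day 180, and Table 6 has an unscheduled column. Consent at an unscheduled Day 175 visit would leave 175 − 107 = 68 days, or 68/73 = 93%. Consent at Day 180, allowed by Sections 6.1 and 6.3, would leave all 73.

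**Bound on the understatement.** Let A be the number of subjects who truly have an event in the extension window, and L the share of those A who consented late. Only late consenters can lose an event, so the reported number is at least A(1 − L), and the relative understatement of a crude percentage is at most L. This needs no assumption about hazards. If risk is the same in early and late consenters, L equals the late-consent share s.

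**Range for s.** The documents do not give s, so these values are assumptions: for s = 0%, 10%, 25% or 50%, the relative understatement is at most 0%, 10%, 25% or 50%. The share of extension-period events lost, with a constant event rate and every late consenter signing at Day 140, is s × 33/73 = 0%, 4.5%, 11.3% or 22.6%.

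**Full-period summary.** A child with any AE before Day 107 already counts in an any-AE percentage over 180 days, so that summary is less affected.

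**The case against.** The best defence is that the footnotes come in mirrored pairs and read naturally as bookkeeping between two databases. Consent to both studies may be signed on the same day, and without such a rule the same event could be entered twice. The consent rules say when MSB-GVHD002 starts, footnote k says which study owns an event, and the two can nest. This stands. A reader might infer that the protocol flatly contradicts itself, but the text does not force that. Under the nested reading, however, the uncovered interval remains.

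A reader might also count Sections 6.1.1.1 and 6.1.1.6 as demanding pre-consent events. The first says "Significant new findings made after the Day 100 visit that meet the definition of an AE or SAE must be recorded", but it concerns the study's physical examinations. The second says (S)AEs "will be collected at each assessment time point", which ties collection to assessments. Neither sets an onset-date rule, and neither is relied on here.

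For medications some look-back is already planned: Section 6.1 lists prior as well as concomitant medications, Section 6.4 covers prior second-line drugs, and Section 6.5.2 asks for new treatments from Day 100. The gap is therefore smaller there than for AEs.

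It is also tempting to say that the events will be lost. Sections 6.3 and 7.1.1 state when collection begins, not that earlier onsets are barred; only Section 8 is worded by date of occurrence. The eCRF completion guidelines cited in Section 15.4, the consent form, the MSB-GVHD001 protocol and the separate SAP promised in Section 9.1 are not visible, and any of them might supply an instruction or longer SAE follow-up. The number of late consenters may be zero.

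**Conclusion.** The point holds as a gap in the visible text, with moderate confidence. For a child who consents after about Day 107, AEs and SAEs with onset before consent are not clearly collected by either study, and no visible section sets up retrospective recording. The uncovered time is 13 to 53 days for consent at the Day 120 to Day 160 visits, and nearly all or all of the 73 days for consent later than that.

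The consequence is a possible understatement of the extension-period AE/SAE summary. Its size is unknown, because neither the late-consent share nor the event rate is given. It cannot exceed the share of subjects with an event who consented late. This assumes a crude percentage over the whole Safety Population; Section 9.4.1 speaks of numbers and rates without fixing a denominator. Section 9.9 rules out imputation for safety in general, so nothing downstream would fill the gap.

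The documents do not support calling this an outright contradiction, a certain loss of data, or a bias of any stated size. The point makes no claim about deaths before consent, or about time to flare or to second-line therapy.

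**What to change.** 1. State in Sections 6.3, 7.1.1, 8 and 9.4.1 that, at consent, the site records from source documents all AEs and SAEs with onset from Day 107, together with hospitalisations, transfusions, and any concomitant medications not already captured as prior medications. Flag these entries as retrospective in the eCRF, and make sure the consent form permits the abstraction.
2. Reconcile Table 6 footnotes a and k with Sections 6.1, 6.3, 7.1.1, 8 and 9.4.1. This includes the latest permitted consent (before Day 180 or through it) and whether footnote k is a collection rule or only an allocation rule.
3. Report the number of subjects under AE observation in each visit interval, so that time not recovered is not counted as event-free.

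The cost is a sentence in four sections, footnote edits, a consent-form line, an eCRF flag, and chart abstraction for late consenters only. The drawback is that non-serious AEs gathered retrospectively will be less complete than those gathered prospectively, which is why they should be flagged. If the eCRF guidelines or the MSB-GVHD001 protocol already provide for this, a cross-reference to them may be enough for the first item.

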## 6.4 Background and Prior Second-Line Medication

Background and prior second-line medications will be coded using the most recent WHO Drug Dictionary (WHO-DD) and summarized by ATC code.

## 6.5 Concomitant Medication and Supportive Therapy

### 6.5.1 Standard of Care for aGVHD

All enrolled subjects will continue to receive institutionally defined standard of care (i.e., maintenance of steroid treatment and other prophylactic treatment for aGVHD) as described in MSB-GVHD001.

Investigators should provide standard of care treatment for viral infections as appropriate, including prophylaxis and treatment if there is evidence of viral reactivation and/or infection.

### 6.5.2 Concomitant Medications

Subjects may continue to be treated with systemic steroid therapy and receive any second-line therapy as necessary at the discretion of the Investigator and per institutional guidelines.

Information on all concomitant medications and therapy will be collected for this study. All new pharmacologic and non-pharmacologic treatment used by study subjects from Day 100 to Day 180 should be recorded in the corresponding CRF. Concomitant medications will be coded using the most recent WHO Drug Dictionary (WHO-DD) and summarized by ATC code.

### 6.5.3 Steroid Taper

If continued steroid therapy is required, the dosing of methylprednisolone or equivalent may be tapered at the discretion of the Investigator. A steroid taper rate of at least 10% of the dose per week but not to exceed 25% of the dose per week is recommended as described in [Appendix 6](#), with the goal of discontinuing steroid by 10 weeks after initiating taper.

### 6.5.4 Escalating Therapy

Protocol guidelines for escalating therapy of aGVHD for worsening disease include:

1. Worsening of symptoms for at least 3 days, or
2. Grades C-D aGVHD persisting for at least 1 week despite treatment, or
3. Grade B aGVHD persisting for at least 2 weeks despite treatment.

Escalation of therapy does not constitute withdrawal of a subject from the study. If escalation of therapy occurs, the subject is to continue on study and receive all assessments per protocol.

### 6.5.5 Supportive Care

In addition to prescribed investigational agent plus corticosteroids and prophylactic therapies, all subjects may receive the following:

- Transfusion support per institutional practice. Type of transfusion and the number of units will be recorded in the eCRF.
- Anti-infective prophylaxis directed towards: CMV, gram positive (encapsulated) bacteria, pneumocystis carinii and fungal infections per institutional practice.

## 7. SAFETY GUIDANCE

### 7.1 Definitions

#### 7.1.1 Adverse Event

An AE is defined by the International Conference of Harmonization (ICH) guideline for Good Clinical Practice as any untoward medical occurrence in a subject administered a pharmaceutical product and which does not necessarily have a causal relationship with the treatment.

An AE can therefore be any of the following:

- Any unfavorable and unintended sign (including an abnormal laboratory finding), symptom, or disease temporally associated with the use of a medicinal product, whether or not considered related to the medicinal product
- Any new disease or exacerbation of an existing disease (a worsening in the character, frequency, or severity of a known condition)
- Recurrence of an intermittent medical condition (e.g., headache) not present at baseline
- Any deterioration in a laboratory value or other clinical test (e.g., ECG, X-ray) that is associated with symptoms or leads to a change in study treatment or concomitant treatment or discontinuation from study drug.

Adverse events that are related to a protocol-mandated intervention, including those that occur prior to assignment of study treatment (e.g., screening procedures such as biopsies etc.) are to be reported.

Collection of all AEs will begin upon signing of the informed consent form (ICF). Pre-existing conditions that **worsen** during a study are to be reported as AEs.

